- **Cincinnati** - Cincinnati Children's Hospital Medical Center
- **Aurora** – University of Colorado SOM and Children's Hospital Colorado
- **Houston** – Baylor Medical College and Texas Children's Hospital
- **Indianapolis** – University of Indiana and Riley Hospital for Children
- **Minneapolis** – University of Minnesota
- **Seattle** – University of Washington and Seattle Children's Hospital
- **St Louis** - Washington University and St Louis Children's Hospital
- **Toronto** - The Hospital for Sick Children and University of Toronto

Fibroscan is available through the NIH at the bolded centers. Baltimore and Minneapolis and St Louis do not have Fibroscan available at this time. If it becomes available, they will participate in this study.

The CFLD NET study is supported by the ChiLDReN Data Coordinating Center (DCC) at the University of Michigan/Arbor Research and the clinical component is funded by the CF Foundation

Study Aims and Hypotheses

- Primary Objective:
- Aim 1:
 - To determine if transient elastography (TE), when combined with ultrasound (US) pattern characterization can improve the prediction of progression to a nodular pattern on US.
 - - o Hypothesis 1: TE results can differentiate children with a heterogeneous or homogeneous patterns on grayscale liver US who will progress to a nodular pattern on US
- Secondary Objectives
- Aim 2: To confirm the feasibility of obtaining TE measurements in children with CF
 - o Hypothesis 2a: Valid TE measurements will be obtained in more than 90% of children with CF
 - o Hypothesis 2b: To determine the variability of TE measurements taken at different liver sites in the same patient
- Aim 3: To prospectively assess whether TE data are associated with conventional markers of hepatic fibrosis and portal hypertension
 - o Hypothesis 3: TE based values will correlate with conventional biomarkers of fibrosis/liver disease severity in CF: APRI, Fib-4, platelet count and spleen size
- Exploratory Objectives:
- Aim 4: To determine if TE with fat content can improve assignment of grade in situations where there is a dichotomy of radiology grades (i.e. 2 HTG, 2NL)

August 12, 2016

- Hypothesis 4a: The combination of grayscale liver US image pattern assessment and TE values with fat content will differentiate between those individuals with dichotomous radiology grades (2HTG/2NL 2HTG/2HMG or 2HTG/2CIR) and risk of progression to a nodular pattern on US.

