- Hypothesis 4b: Higher fat content will be associated with a lower risk of progression to a nodular pattern on US
-
- Aim 5: To determine if TE can predict the development of portal hypertension and its complications in children and young adults with CF and a nodular pattern on US.
 - Hypothesis 5: Among those children with a nodular pattern on US, TE results will correlate with clinical findings of portal hypertension (splenomegaly, thrombocytopenia, variceal hemorrhage and/or ascites)
- Aim 6: To pilot the correlation of TE and hepatic fibrosis and fat content in children and young adults with CF who have a clinically indicated liver biopsy.
 - Hypothesis 6: TE assessment of liver stiffness and fat content will correlate with steatosis and fibrosis staging on liver biopsy in CF

Inclusion/Exclusion Criteria

Inclusion criteria:

- Participants enrolled in CFLD NET PUSH study in longitudinal follow up at centers with Fibroscan available (currently 8/11 centers)
- Entry criteria for that study were:
 - CF as determined by sweat chloride >60 meq/l
 - Pancreatic insufficiency
 - Age 3-12 years old at entry
 - For entry into the longitudinal follow up subjects were in one of two groups
 - A screening US pattern of nodular liver (CIR), heterogeneous increased echogenicity (HTG) or homogeneous increased echogenicity (HMG)
 - A screening US pattern of normal (NL) matched to a HTG subject (2 NL:1HTG) by age, center and pseudomonas status

Exclusion criteria:

- Exited from the PUSH Study
- Unable / unwilling to sign consent

Recruitment, enrollment and follow-up

- Planned minimum follow up 2 years
- Recruitment period: November 1, 2016 to October 31, 2019
- Total sample size 200 subjects assuming a 90% success

US pattern	Subjects in Study at	Potentially available
------------	----------------------	-----------------------

August 12, 2016

	centers with TE	subjects at centers currently without TE
NL	90	38
HTG	33	6
HMG	19	3
CIR	24	11

Study Procedures

The research protocol will encompass the prospective longitudinal analysis of FibroScan measurements of liver stiffness in children with CF who are enrolled in the PUSH study. Visits will occur annually for at least two years, therefore there will be a minimum of three assessments, a baseline and at least two annual follow up visits.

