At each visit the comprehensive clinical data and biosample collections will occur according to the PUSH protocol. Research US is performed every 2 years. FibroScan measurements will be done using a standardized protocol at each of these visits by a designated CFLD NET investigator with a specialized CRF completed for the Fibroscan measurements.

One or two investigators will be trained at each site to perform TE measurements to ensure consistent and standardized acquisition of complete data. Fasting will be specified for these procedures. While fasting requirements can significantly complicate pediatric-based studies, adult data suggest that fasting can affect elastography values (6, 7). We have been successful with fasting for the Doppler US evaluations in this study and have processes in place to successfully do studies in fasted individuals. Thus we will plan for a minimum of a 4 hour fast for the TE. The exam time is estimated to be 10-20 minutes. No lower limit age restrictions are incorporated in this protocol to afford an accurate assessment of feasibility in children of all ages (the youngest subject in the study is currently 5 years old). No sedation is needed for TE assessments.

Schedule of Visits

Procedure	Baseline	12 months	24 months
Informed Consent	X		
TE Measurement	X	X	X
TE CRF	X	X	X
Clinical data per PUSH	X	X	X
Biospecimens per PUSH	X	X	X
Research US per PUSH (occurs every 2 years, will vary on entry phase)	US will be performed on the ongoing schedule. TE will be timed to coincide with annual bloodwork and clinical visit.		

August 12, 2016

Data Collected

Clinical and laboratory data including laboratory values, physical examination, medical history, ultrasound, and biosamples will be collected per the PUSH protocol. Additional liver biopsy results will also be collected for patients enrolled in this proposed ancillary study.

Transient Elastography (FibroScan®) measurements

Up to 6 personnel will be trained at each site to perform FibroScan™ measurements to ensure consistent and standardized acquisition of complete data. While we will focus on one or two personnel involved in PUSH at each center, FibroScan™ will be available at ChiLDReN centers for multiple studies with more investigators trained. By allowing up to 3 investigators per site, we will reduce the likelihood of missing any measurements on eligible subjects. Training will take place at each site by a designated trainer from EchoSens.

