- “Controlled Attenuation Parameter (CAP)” quantifies liver steatosis and is measured in dB/m (median of 10 subsequent valid measurements).

In addition quality control data are collected:

- Invalid measurements and success rate
- Number and list of valid measurements
- Inter quartile range (IQR) (kPa or dB/m) of all valid measurements within the examination (reflects the dispersion of stiffness or CAP measurements)
- IQR/med. (%) Indicates the IQR/median ratio and should remain as low as possible to ensure reliable results (goal < 30%)

Study withdrawal/discontinuation

The participant and/or participant’s family may withdraw from the study at any time. The study investigator can withdraw the participant from the study at any time if that is felt to be in the best interest of the participant and/or their family. If a participant in the longitudinal follow up study meets an endpoint for the end of the PUSH study (liver transplantation or death) they will have met the end of this study.

Statistical and Design Considerations

Based upon interest and involvement of the subjects in PUSH, we anticipate all subjects currently available (168) will enroll. If TE becomes available at the 3 centers without TE, then up to an additional 60 subjects would be available to enroll. TE would be available from all eligible US pattern subjects.

Hypothesis 1: TE results can differentiate children with a heterogeneous or homogeneous pattern on grayscale liver US who will progress to a nodular pattern on US

Analysis:

To test whether TE, when combined with US pattern characterization can improve the prediction of progression to a nodular pattern on US, we will build two discrete survival models using logistic regression. In the first model, greyscale US consensus grade will be used to predict prediction to nodular pattern. In the second model, we will add the predictor liver stiffness measured by TE. If the second model significantly increases the area under the receiver operating characteristic curve

August 12, 2016

(AUROC) comparing to the first model, we will conclude that TE can improve the prediction of progression to a nodular pattern on US. All subjects graded as NL, HMG, or HTG at the time this ancillary study starts will be included in the analysis.

Power calculations:

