For this analysis we will include all subjects with a nodular US pattern (CIR). The primary outcome will be a composite outcome defined as occurrence of any of the following three endpoints:

August 12, 2016

Hypersplenism: platelets <150,000
Variceal hemorrhage
Splenomegaly as indicated by a palpable spleen
Ascites as clinically detected ascites

A discrete survival analysis using logistic regression will be used to test whether transient elastography results are associated with risk of developing liver cirrhosis complications. The predictor will be most recent TE results.

Power calculation:

Previous literature has reported mean a rate of variceal hemorrhage between 5 and 10% per year with CF and cirrhosis. There is no data for rates of development of splenomegaly or thrombocytopenia in CF with a nodular US pattern. With currently 33 subjects with a nodular US pattern and 90% successful rate of TE, we anticipate 3 to 6 subjects (10% ~20%) among 30 subjects developing one of the endpoints in 2 years. We assume the true difference in population mean TE measurements is 19 kPa between subjects with and without portal hypertension; we assume the SD is 22.0 kPa and 6.0 kPa for subjects with and without portal hypertension, respectively. Our calculation shows that using 2-sided likelihood ratio Chi-square test (Type I error rate 5%) there will be 80% power to detect odds ratio 4 ~ 5 per 10kPa increase in TE results.

Hypothesis 6: TE assessment of liver stiffness and fat content will correlate with steatosis and fibrosis staging on liver biopsy in CF

Analysis: ANOVA or Kruscal-Wallis test, whichever is appropriate, will be used to compare TE measures between groups based on steatosis and fibrosis staging on liver biopsy in CF.

Human research participant issues

Institutional Review Board Approval

Local institutional review board approval will be obtained for the study. IRB approvals will be centrally collated at the Data Coordinating Center.

Standard of Care

Standards of care for the management of liver disease at each of the CFLD NET sites will be followed. At present there are no clinical standards for interventions based on TE-measured liver stiffness for pediatric CF patients and thus there are no expected interventions based solely on TE measurements.

Consent

Informed consent and assent (when appropriate according to local standards) will be obtained prior to any research activities. A common template for

August 12, 2016

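### The Hypothesis 1 risk set is fixed by ultrasound grade at study start, so it admits children already graded nodular at or before their first TE, and nothing excludes those events

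*Protocol*

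**What the plan says.** Under Statistical and Design Considerations, Hypothesis 1, the protocol plans a comparison of prediction with and without TE: "we will build two discrete survival models using logistic regression". The first model uses the ultrasound grade. For the second, "In the second model, we will add the predictor liver stiffness measured by TE". Membership of the analysis set is then fixed by one sentence, repeated for Hypothesis 4b: "All subjects graded as NL, HMG, or HTG at the time this ancillary study starts will be included in the analysis".

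Three other parts of the protocol set the timing:

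- Recruitment, enrollment and follow-up: "Recruitment period: November 1, 2016 to October 31, 2019". The synopsis gives dates one year earlier, but the window is also 36 months.
- Study Procedures: "Research US is performed every 2 years".
- Schedule of Visits: "US will be performed on the ongoing schedule. TE will be timed to coincide with annual bloodwork and clinical visit". Consent and the first TE both fall in the baseline column, that is, at each child's own entry.

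Children with a nodular (CIR) pattern are eligible for enrolment and are the population of Hypothesis 5. A child who becomes nodular before entering the TE study is therefore not turned away.

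**The concern.** A prediction analysis needs one time zero at which the child is free of the outcome and the predictor is measured, with events counted only afterwards. Here freedom from the outcome is judged at one date and the predictor is measured at another, possibly much later. Nodular grades given between the two dates, or on the day of the first TE, are admitted.

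For such a child a high stiffness value shows that TE recognises a nodular liver. It does not show that TE foresees one. The protocol's Background notes that preliminary studies suggest TE identifies children with advanced liver disease, so the error would favour TE. With roughly 9 expected progressions, one or two misplaced events carry weight.

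**Working it through.** **1. Can a child be graded CIR before the first TE and stay in the set?** Take a child graded HTG at study start, graded CIR at a PUSH ultrasound the next year, and enrolled for TE after that. The child meets the analysis rule (HTG at study start), may enrol (CIR is not an exclusion) and has the outcome (progression to nodular). No sentence under Hypothesis 1 requires a non-nodular ultrasound at first TE, or a TE before the event. Nor does it say which TE enters the model. Only Hypothesis 5 does: "The predictor will be most recent TE results".

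**2. How many children have a research ultrasound between study start and first TE?** Assume the next ultrasound is uniform over 0 to 24 months and first TE occurs at month E. The chance is the mean of min(E/24, 1).

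- E uniform over 0 to 12 months: 6/24 = 25%.
- E uniform over 0 to 36 months: [24 × 0.5 + 12 × 1]/36 = 24/36 = 67%.

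These are children with any ultrasound in the gap, not children graded CIR.

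**3. How many progressions could fall in the gap?** From the Hypothesis 1 power paragraph and the table of available subjects: 33 HTG at 20%, and 90 NL + 19 HMG = 109 at 2%. Expected events: 33 × 0.20 + 109 × 0.02 = 6.60 + 2.18 = 8.78. The protocol mentions a 2-4 year horizon for HTG progression but ties no horizon to the 20%, so both ends are shown. Events before TE = 8.78 × mean lag / horizon:

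| Mean lag from study start to first TE | 4-year horizon | 2-year horizon |
|---|---|---|
| 0.5 year | 1.1 | 2.2 |
| 1 year | 2.2 | 4.4 |
| 1.5 years | 3.3 | 6.6 |

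A mean lag of 0.5 year matches enrolment of everyone over 12 months; 1.5 years matches uniform enrolment over 36 months. Cross-check of the first row: 25% of children with an ultrasound in the gap × 8.78 = 2.2 if 20%/2% are two-year risks.

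**4. What would the bias do if those events were paired with a later TE?** A simulation (2,000 runs per setting) gave TE no predictive value: 142 children, risks 20%/2%, stiffness lognormal(0, 0.5) as in the protocol. Stiffness was multiplied by 1.5, 2 or 3 in children already nodular at first TE. The multipliers are assumptions; the protocol gives none. False-positive rates at nominal two-sided 5%:

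| Share of events before TE | Likelihood ratio test (×1.5, ×2, ×3) | DeLong test of AUROC gain (×1.5, ×2, ×3) |
|---|---|---|
| none | 5-7% | 5-6% |
| 12.5% (about 1 event) | 8%, 12%, 19% | 5%, 7%, 7% |
| 25% (about 2 events) | 11%, 21%, 38% | 8%, 10%, 11% |

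**5. What does removing those events cost?** The protocol's 80% power (odds ratio 4 per unit, 142 children) reproduces as 80.4% by simulation if 20%/2% are the risks at median stiffness, with 12.3 expected events. If they are average risks, with 8.8 events as in step 3, power is 70%. Two-sided 5% is assumed, since the Hypothesis 1 paragraph states no level. From 70%, removing 12.5% or 25% of events leaves about 69% or 63%.

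**The case against.** The strongest reply is that the protocol never says an event before TE will be paired with that later TE. In a discrete survival model an interval that ends before any TE has no stiffness value, and such intervals might drop out. Hypothesis 5, with the same model type, looks back to the latest TE. This stands: a reader might infer that early nodular grades will be counted as predicted progressions, but the text supports only that they are admitted and that nothing excludes them.

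Second, the start of the study could mean each child's own baseline. That reading shrinks the gap without closing it, because the grade in force could still come from an ultrasound up to two years before the TE, and a CIR grade on the day of first TE is still not dealt with.

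Third, these are existing PUSH participants, all expected to enrol, with TE tied to annual visits. First TE at the next annual visit is the natural expectation, which makes the 25% case and the half-year lag likelier than the 67% case. This also stands.

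Fourth, such details often sit in a statistical analysis plan. That covers the choice of TE per interval, but the protocol states an inclusion rule, and the rule itself is misaligned.

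Three stronger readings are tempting and unsupported:

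- That about half of all progressions predate TE, because ultrasounds are two years apart. If the CIR grade comes after TE, TE did precede the defined endpoint, which is a pattern on ultrasound. Undetected earlier onset is ordinary interval censoring.
- That lower power measures the harm. It measures the cost of the correction.
- That including NL children is part of this error. Hypothesis 1 speaks of children with HTG or HMG patterns, but Aim 1 is not so limited and the power calculation deliberately includes about 63% NL. That is a separate matter from timing.

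**Conclusion.** The concern holds as a misalignment of time zero in the primary analysis and in Hypothesis 4b. The inclusion rule lets in children graded CIR before or at their first TE, and no other provision removes those events. The direction of the possible bias is upward for TE.

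Its size cannot be determined from the protocol. At a mean lag of half a year, roughly 1 to 2 of about 9 expected progressions would precede first TE, and more at longer lags. These counts assume evenly spread progression and the protocol's 20% and 2% as average risks; the 25% and 67% figures assume uniform ultrasound phase and the stated enrolment patterns. The false-positive rates apply only if the early events are paired with a later TE, and they rest on assumed stiffness multipliers.

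The wording should be corrected, because the question is the primary one and the correction is cheap. The documents do not show that the planned analysis is certain to be biased.

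**What to change.** Change the analysis wording for Hypothesis 1, and identically for Hypothesis 4b:

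1. Start each child's risk time at the first valid TE.
2. Include the child only if the latest research ultrasound on or before that TE is graded NL, HMG or HTG.
3. Count as progression only a CIR grade on a later research ultrasound.
4. In each interval use only TE measured before the ultrasound that defines the outcome.
5. As a sensitivity analysis, limit the set to children whose baseline ultrasound is close in time to the first TE, with the allowed gap stated in advance. This addresses the older baseline grades that the main rule still permits.

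The cost is the loss of a few events and slightly lower precision. No extra procedure or visit is needed. Moving the first TE to a visit with a research ultrasound would tighten the alignment further, but it is optional and could delay first TE for some children.

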The estimated 2-4 year progression rate is ~40% in HTG subjects. Thus of the 33 available with HTG pattern, 10-13 would be predicted to progress to CIR. However, as the study is in progress, ~20% have progressed so the risk of progression may be lower. We choose to make a conservative assumption in our power calculation: 20% of HTG subjects will progress to CIR pattern, and 2% of NL or HMG subjects will progress to CIR pattern. In addition, we assume the liver stiffness measure follow a lognormal distribution with location =0 and scale parameter =0.5 (i.e. median=1, Q1=0.71, Q2=1.4). With 142 subjects (approximately 63% NLs, 23% HTGs, and 13% HMGs) we will have 80% power to detect an odds ratio of 4 for a 1 unit increase in the liver stiffness measure. (Caveat: Given that we do not have any preliminary data of TE measures in CF subjects, the results of this power calculation only give us a general guidance).

Hypothesis 2a: Valid TE measurements will be obtained in more than 90% of children with CF

Analysis:

For hypothesis 2a, we will estimate the proportion of subjects in whom a valid transient elastography measurement can be obtained. At each site, all measurements will be performed by one of the trained examiners. The results will be reported as the median of 10 valid measurements and will be accepted as valid if the ratio of the interquartile range (IQR) and median was < 30% and the success rate was > 60% (8, 9). Per Goldschmidt 2013 (9) we will define two measures of the feasibility of transient in our population: “technically possible” and “acceptable quality.” The proportion of subjects with a “technically possible” FibroScan™ is defined as the number of subjects with at least 10 FibroScan™ measurements obtained divided by the number assessed. The proportion of subjects with FibroScans™ of “acceptable quality” is defined as the number of subjects with FibroScan™s with the ratio of the interquartile range and median of the 10 measurements <30%, divided by the number assessed. The proportions and their 95% confidence intervals will be provided using the Wald method. We will do a stratified (separate) analysis by <8 years of age and >8 years of age. There will be the opportunity to compare this data to children with other liver diseases in the ChiLDReN FORCE study.

Hypothesis 2b: To determine the variability of TE measurements taken at different liver sites in the same patient

Analysis

August 12, 2016

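### Wald 95% intervals are prescribed for feasibility proportions expected above 90%, where they under-cover and have zero width at 100%; the age strata also leave out age 8

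*Protocol*

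**What the plan says.** The place is the protocol, Statistical and Design Considerations, Hypothesis 2a. The hypothesis reads "Hypothesis 2a: Valid TE measurements will be obtained in more than 90% of children with CF". Two proportions are defined over the children assessed. The technically possible proportion is "the number of subjects with at least 10 FibroScan™ measurements obtained divided by the number assessed". The acceptable-quality proportion counts children with "the ratio of the interquartile range and median of the 10 measurements <30%, divided by the number assessed".

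The interval method is then fixed: "The proportions and their 95% confidence intervals will be provided using the Wald method". The next sentence adds the age breakdown: "We will do a stratified (separate) analysis by <8 years of age and >8 years of age". The section says nothing about success in every child, and it gives no stratum sizes.

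On the overall denominator, the Design Synopsis table lists 166 children at centers with TE. The opening of the statistical section says "we anticipate all subjects currently available (168) will enroll". The recruitment section gives "Total sample size 200 subjects assuming a 90% success".

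**The concern.** The Wald interval takes its standard error from the observed proportion. As that proportion nears 1 the estimated standard error shrinks towards zero, so the interval becomes too short just where the hypothesis places the result. Its misses are also one-sided: most of them occur because the whole interval lies above the true value, which makes feasibility look more certain than the data allow. If every child succeeds, the interval runs from 100% to 100% and claims certainty from a finite sample. Near that point the upper limit passes 100%.

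The method is named in the protocol, so this is not a detail left open for a later analysis plan. At stake is the uncertainty reported for the feasibility aim, most of all within age groups. Separately, the two strata as worded have no place for a child aged 8.

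**Working it through.** **Inputs.** n = 166 (Design Synopsis table), with 168 (statistical section) as a check; z = 1.96; the target of 90% from Hypothesis 2a. True proportions of 90%, 95%, 97% and 99% are scenarios spanning the hypothesised range. Only 90% is a protocol figure. The protocol gives no precision or interval width for this hypothesis, so there is no stated figure to reproduce.

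**Formulas.** With p̂ = x/n:
- Wald: p̂ ± z√(p̂(1−p̂)/n).
- Wilson: [p̂ + z²/(2n) ± z√(p̂(1−p̂)/n + z²/(4n²))] / (1 + z²/n).
- Exact coverage at true p: the sum of binomial probabilities of every x whose interval contains p.

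**Example, n = 166, true p = 95%.** The Wald interval contains 95% for x = 151 to 161. P(X ≥ 162) = 7.8% (interval wholly above the truth) and P(X ≤ 150) = 0.9% (wholly below). Coverage is 100 − 7.8 − 0.9, or 91.2% before rounding of the two parts.

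**Coverage at the documented size.**

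| True p | Wald, n=166 | Wilson, n=166 | Wald, n=168 | Wilson, n=168 |
|---|---|---|---|---|
| 90% | 93.5% | 94.9% | 93.8% | 94.8% |
| 95% | 91.2% | 95.1% | 91.6% | 94.8% |
| 97% | 87.3% | 96.5% | 87.7% | 96.3% |
| 99% | 81.0% | 97.4% | 81.4% | 97.2% |

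Clopper-Pearson coverage at n = 168 is 96.0%, 96.9%, 98.1% and 99.3% for the same four values.

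**At the boundary.** For 166/166, p̂(1−p̂) = 0, so Wald gives 100% to 100%; Wilson gives 97.7% to 100% and Clopper-Pearson 97.8% to 100%. For 165/166, Wald gives 98.2% to 100.6%.

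**If the lower limit were compared with 90%** (the protocol does not say that it will be). At n = 166 the Wald lower limit first exceeds 90% at x = 156 (90.4%; Wilson 89.3%), and the Wilson lower limit at x = 157 (90.02%). At a true 90%, P(X ≥ 156) = 5.0% and P(X ≥ 157) = 2.6%, against a nominal 2.5%. The two methods disagree at one outcome only, 156/166. At n = 168 that outcome is 158/168.

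**Age strata (sizes assumed, for illustration only), true p = 95%.**

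| Assumed n | Wald | Wilson |
|---|---|---|
| 20 | 63.9% | 92.5% |
| 30 | 78.2% | 93.9% |
| 40 | 86.8% | 95.2% |

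**Age 8.** Entry to the parent study was at 3 to 12 years, and "the youngest subject in the study is currently 5 years old" (Study Procedures), so age 8 lies within the range studied. With age in completed years, a full year of children falls in neither stratum. With exact age, almost nobody does.

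**The case against.** The strongest reply is that little turns on this. Hypothesis 2a is secondary, and its analysis is framed as estimation: a proportion and an interval are to be reported, with no test or success threshold. A reader might infer that the lower limit decides whether the 90% claim is met, and so that Wald inflates a false-positive rate. The protocol sets no such rule, either overall or within age groups. The 5.0% above is therefore the error of a hypothetical reading, not of the plan. Even under that reading, the methods part at a single outcome at n = 166. For 158/166, Wald gives 91.9% to 98.4% and Wilson 90.8% to 97.5%, both above 90%. At the protocol's planning value of 90% success, the coverage shortfall is mild.

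A reader might also take it as settled that the under-8 group is small and its intervals badly wrong. A small group is plausible given the entry ages, but no age distribution is given, so the stratum figures only illustrate.

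The age-8 gap looks like a drafting slip. The intended split is clear, and the children concerned stay in the overall estimate. A sign lost when the text was read from the PDF cannot be excluded, although a less-than-or-equal sign survives in the probe-selection rule.

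All of this stands and limits the importance. It does not rescue the method: the intervals would carry a 95% label that they do not meet at the proportions examined, and complete success would be reported with no uncertainty.

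**Conclusion.** The point holds, with modest importance. At n = 166, Wald coverage falls from 93.5% at a true 90% to 81.0% at 99%, while Wilson stays between 94.9% and 97.4%. The zero width at 100% success holds for any n. These results rest only on binomial sampling and the documented cohort size. The larger shortfall within strata, about 64% to 87% coverage at a true 95%, depends on an assumed 20 to 40 children. The documents do not support a claim that the feasibility conclusion itself would be wrong: there is no lower-limit rule, and the point estimates are unaffected. The omission of age 8 is a minor wording fault.

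**What to change.** In the Hypothesis 2a analysis, replace the Wald method with Wilson intervals, or Clopper-Pearson if guaranteed coverage is preferred, for both feasibility proportions, overall and by age stratum. Write the strata as <8 and ≥8 years. The change takes two short edits and affects neither data collection nor sample size. Its cost is slightly lower lower limits: for 158/166, 90.8% with Wilson against 91.9% with Wald.
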